### **6.2 Selection Criteria**

#### **6.2.1 Inclusion Criteria**

Subjects accepted for this study must:

1. Be over 18 years of age
2. Be able to communicate effectively with the study personnel
3. Have histologically confirmed prostate cancer
4. Have been treated with an LHRH agonist or LHRH antagonist for at least the 2 months prior to randomization
5. Be continued on an LHRH agonist or LHRH antagonist throughout this study (must be continuous therapy)
6. Have experienced hot flashes for at least one month prior to study entry
7. Have moderate or severe vasomotor symptoms (hot flashes) (defined as a minimum of 4 moderate to severe hot flashes per day or 12 per week at baseline)
8. ECOG performance status of 0 to 2
9. Be willing to use electronic data capture for the relevant medical events
  - Must be at least 80% compliant during the screening period (for the 14 contiguous day hot flash assessment that is required during screening)
10. Subjects must agree to use acceptable methods of contraception
  - If their female partners are pregnant or lactating, acceptable methods of contraception from the time of the first administration of study medication until 6 months following administration of the last dose of study medication must be used. Acceptable methods are: Condom used with spermicidal foam/gel/film/cream/suppository. If the subject has undergone surgical sterilization (vasectomy with documentation of azospermia), a condom with spermicidal foam/gel/film/cream/suppository should be used
  - If the male subject's partner could become pregnant, use acceptable methods of contraception from the time of the first administration of study medication until 6 months following administration of the last dose of study medication. Acceptable methods of contraception are as follows: Condom with spermicidal

foam/gel/film/cream/suppository [i.e., barrier method of contraception], surgical sterilization (vasectomy with documentation of azospermia) and a barrier method {condom used with spermicidal foam/gel/film/cream/suppository}, the female partner uses oral contraceptives (combination estrogen/progesterone pills), injectable progesterone or subdermal implants and a barrier method (condom used with spermicidal foam/gel/film/cream/suppository)

- If the female partner has undergone documented tubal ligation (female sterilization), a barrier method (condom used with spermicidal foam/gel/film/cream/suppository) should also be used

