- Serum hormones ([Appendix A](#))
- Serum chemistry ([Appendix A](#))
- Urinalysis

12. Measurement of frequency and severity of hot flashes utilizing electronic device (values over 14 contiguous days in order to establish a weekly baseline)

- Must be at least 80% compliant during this assessment. This translates into recording frequency and severity of hot flashes at least 11 of the 14 days.

13. Bilateral Doppler ultrasound of the lower extremity (If the subject is diagnosed with a VTE in this assessment, the subject will not be eligible for the study under the exclusion criterion of history of a VTE).

Patients that have been previously screened for this study and could not complete screening for reasons other than not meeting the inclusion and exclusion criteria, may be rescreened into the study. Laboratory testing conducted under this protocol ([Appendix A](#)) within 45 days prior to randomization into this study, may be used as the baseline laboratory values for this study and repeat laboratory testing is not required unless new coadministered medication(s) has been started, unless the investigator determines that retesting is warranted.

Patients that failed screening under previous versions of the protocol due to a positive lupus anticoagulant, but in whom lupus anticoagulant was not “detected” may be rescreened under Amendment 2, Version 7.0 of the protocol.

Patients that failed screening under previous versions of the protocol due to indeterminate cardiolipin antibody, may be rescreened under Amendment 2, Version 7.0 of the protocol.

Patients that failed screening under previous versions of the protocol due a finding related to Protein C or Protein S, including patients that were excluded from participation inappropriately due to elevated levels of Protein S and/or Protein C above the upper limit of normal, may be rescreened under Amendment 2, Version 7.0 of the protocol.

For patients that fall into the three categories outlined above, laboratory testing conducted under this protocol ([Appendix A](#)) within 45 days prior to randomization into this study, may be used as the baseline laboratory values for this study and repeat laboratory testing is not required unless new coadministered medication(s) has been started or if the investigator determines that retesting is warranted.

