### **11.3 Appendix C: Hot Flash Assessments**

Assessments of hot flashes will be made at baseline (14 contiguous days during screening) and daily from Day 1 (first dose) to the end of the study. Patients will record frequency and severity of hot flashes using an electronic diary (eDiary) to ensure attributable, time stamped data collection in an unsupervised environment. When experiencing a hot flash the subject will indicate on the app that they have had a hot flash and then will assign a severity to the hot flash based upon the following scale:

- A. MILD:** sensation of heat without sweating
- B. MODERATE:** sensation of heat with sweating, able to continue activity
- C. SEVERE:** sensation of heat with sweating, causing cessation of activity

The hot flashes will then be compiled to examine the number of hot flashes during the period and their severity.

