## 6. STATISTICAL METHODOLOGY

## 6.1 Statistical and Analytical Issues

## 6.1.1 Statistical Methods

For quantitative variables, descriptive statistics will include the number of subjects (n), mean, standard deviation (SD), median, minimum and maximum. Categorical variables will be summarized using the number (n) and percentage (%) of subjects for each category. Unless otherwise specified, the denominator for all percentages will be the number of subjects in the respective treatment group who have data for the respective time point in the applied analysis population. Percentage change from baseline will be calculated using the non-missing (see section 6.1.2) data of both baseline and the respective post-baseline value.

The primary efficacy analyses will only include efficacy data that were captured in the eDiary for hot flashes which were treated with study drug (VERU-944 or placebo). All baseline measurements for efficacy will be collected prior to dosing in the treatment period. By default the frequency and severity of hot flashes at baseline will be determined from the second week of the first two weeks of hot flash eDiary that were recorded; If a patient qualified for the study entry by number of hot flashes during the second week of screening, then data from that week will be used as their baseline. However, if a patient did not qualify for study entry based on the number of hot flashes during that second week then data from the screening week that was used to qualify the patient will be used as their baseline instead. Percentage change from baseline is defined as the post-baseline value of interest minus the baseline value then divided by the baseline value and finally converted to a percentage by multiplying by 100.

A 1-sided alpha level equal to 0.10 will be used to determine statistical significance for the primary and secondary efficacy objectives related to hot flash frequency and severity.

For the treatment period, baseline for the safety assessments will be defined as the Day 1 assessment, or if missing, the last assessment prior to dosing.

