## Data Handling

Baseline week will be determined from the second week of the first two weeks of hot flash eDiary that were recorded; if a patient qualified for study entry by number of hot flashes during the second week of screening, then data from that week will be used as their baseline. However, if a patient did not qualify for study entry based on the number of hot flashes during that second week then data from the screening week that was used to qualify the patient will be used as their baseline instead. A week's data collection will be considered the 6 days prior to plus the day of week's data. For example, Week 6 data will include the data collected for the 7 days from Day 36 through Day 42, inclusive. For a subject's data to be considered non-missing for a given week the subject must have recorded at least 4 days of data during the respective week. For subjects who report at least 4 days of data during a week, the weekly frequency of moderate and severe hot flashes will be the sum across those days of the number of moderate to severe hot flashes. The severity level reported for each of the reported hot flashes will be calculated as follows. Baseline severity level will be the number of severe hot flashes reported times 3 + the number of moderate hot flashes reported times 2 then divided by the number of moderate and severe hot flashes reported. Post-baseline weeks will have their severity level calculated as above but with the addition of reported mild hot flashes so the post-baseline severity for a given week level will be the number of severe hot flashes reported times 3 + the number of moderate hot flashes reported times 2 + the number of mild hot flashes reported times 1 then divided by the number of mild, moderate and severe hot flashes reported. The percentage change from baseline of the frequency of moderate and severe hot flashes will be the number of moderate to severe hot flashes reported for the given week minus the number reported at baseline then divided by the number reported at baseline and converted to a percentage by multiplying by 100. The percentage change from baseline of the severity of moderate and severe hot flashes will be the calculated severity score reported for the given week minus the severity score at baseline then divided by the severity level reported at baseline and converted to a percentage by multiplying by 100.

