#### 6.9 Changes to Methods Planned in the Protocol

At the time the SAP was finalized, there were no changes to methods planned in the protocol. Any other changes from the SAP, including any ad-hoc analysis, will be detailed in the clinical study report.

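### The one-week, switchable baseline costs power and distorts within-arm changes, although 14 diary days are collected; it does not bias the placebo comparison

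*SAP*

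**What the plan says.** **Data collected.** Protocol 8.2, item 12, asks for diary "values over 14 contiguous days in order to establish a weekly baseline", and Protocol Appendix C describes baseline as the same period. The compliance floor is "recording frequency and severity of hot flashes at least 11 of the 14 days". Three days may therefore be missing; if all three fall in one week, that week holds 4 recorded days.

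**Data used.** SAP 6.3.1 states: "Baseline week will be determined from the second week of the first two weeks of hot flash eDiary that were recorded". The exception, also given in SAP 6.1.1, applies "if a patient did not qualify for study entry based on the number of hot flashes during that second week"; in that case "data from the screening week that was used to qualify the patient will be used as their baseline instead". The entry count (Protocol 6.2.1, criterion 7) is a "minimum of 4 moderate to severe hot flashes per day or 12 per week at baseline". A week is valid with 4 or more recorded days. Its frequency is the plain sum over those days, not scaled to 7, and the baseline sum is the denominator of the percentage change.

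**Model and supporting analyses.** The means model in SAP 6.3.1.1 has treatment, week and their interaction, with no baseline covariate. The listed sensitivity analyses change the population or add mild hot flashes; none changes the baseline. SAP 6.3.1.1.1 also plans paired tests of baseline against Week 6 within each arm. SAP 4.2 places randomisation after screening is complete.

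**The concern.** Part of the difference between a man's two screening weeks is chance. Discarding a low second week in favour of the week that passed the count keeps a value that tends to lie above his underlying rate, so he will tend to look improved later whatever he receives. Men who are not switched still have a denominator based on half of the available diary. The same denominator serves every post-baseline week, so borrowing earlier weeks in the MMRM does not average its error away. Incomplete weeks add further error.

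At stake are the power of the primary test, the size of the placebo response and of the other within-arm changes, and the paired tests. Power matters beyond the primary result because SAP 6.7 ties the decision on Stage 2 to statistical significance in Stage 1.

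**Working it through.** **1. The plan's own figure.** With placebo mean m, active mean 0.6m, variance 0.6m, one-sided 0.10 and power 0.90:

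n per arm = 2 × 0.6m × (1.2816 + 1.2816)² / (0.4m)² = 49.3/m

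At m = 12 this gives 4.1, rounded up to 5. At m = 28 it gives 1.8, rounded up to 2. It gives 30 only at m near 1.64. No value of m is stated, so 30 cannot be reproduced. The formula uses mean frequency rather than percentage change, so the baseline rule does not alter it. I take 30 per arm as given.

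**2. Incomplete weeks (arithmetic only).** A 4-day week captures 4/7 = 57% of a steady man's weekly count. A 4-day baseline against a full Week 6 shows 7/4 − 1 = +75% with no true change. A man with 20 a week has 20 × 4/7 = 11.4 in a 4-day second week. If the entry count is also an unscaled sum (the documents do not say), missed entries alone would switch him.

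**3. Unused data, ignoring the switch.** Take weekly values with variance 1 and correlation ρ between any two weeks.

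- Change from one week: 2(1 − ρ).
- Change from a two-week mean: 1 + (1 + ρ)/2 − 2ρ = 1.5(1 − ρ).

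The ratio is 0.75 at any ρ. If the one-week baseline gave 90% power at 30 per arm, the standardised difference would be 2 × 1.2816 × √(2/30) = 0.662. With the two-week mean, power is Φ(0.662/√0.75 × √15 − 1.2816) = Φ(1.678) = 95.3%. Equivalently, 30 × 0.75 = 22.5, so about 23 per arm. This is for an absolute change score.

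**4. The full rule, simulated.** All rates and variability are assumed: lognormal patient rates with CV 0.6, week-to-week CV plus Poisson noise, complete diaries, and entry if either week reaches the threshold. There were 1,000,000 men per setting. Power is for a 40% reduction, 30 per arm, as a two-arm comparison of percentage change at Week 6. Selected settings at 12 a week (each pair is SAP rule / 14-day mean):

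| Median per week | Week CV | Switched | Mean change, switched men, SAP rule, no effect | Mean change, all men, no effect | SD | Power at 0.10 | Power at 0.025 |
|---|---|---|---|---|---|---|---|
| 14 | 0.20 | 16.5% | −18.3% | −6.1 / −0.5 | 40.5 / 38.7 | 99.8 / 100 | 98.9 / 99.6 |
| 14 | 0.50 | 24.3% | −21.4% | −11.2 / +1.4 | 66.8 / 71.0 | 88.2 / 91.4 | 69.4 / 75.4 |
| 20 | 0.35 | 13.5% | −13.7% | +0.3 / +4.2 | 58.4 / 54.3 | 97.2 / 98.9 | 89.0 / 94.5 |
| 35 | 0.20 | 2.9% | −8.2% | +4.8 / +3.1 | 40.8 / 34.6 | 100 / 100 | 99.7 / 100 |
| 35 | 0.50 | 8.5% | −0.3% | +15.8 / +13.0 | 93.2 / 79.4 | 85.2 / 91.5 | 64.3 / 75.7 |

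The 0.025 column is the last Hochberg step in Stage 1. Fifteen settings were run, including a threshold of 28 a week (4 per day × 7). Power with the 14-day mean was equal or higher in all of them: 0 to 6 points at 0.10 and 0 to 11 at 0.025. The variance ratio (14-day / SAP) ran from 0.70 to 1.29. Where it exceeds 1, the SAP rule has pushed baselines up and shrunk the treatment difference too. In the worst case the difference is 30.5 against 36.9 points, and power at 0.025 still rises from 76.5% to 81.4%.

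**5. Missed days and extra day-to-day variation.** A second set of 32 settings used medians 14 to 45 a week and week CV 15–35%, with and without day-level overdispersion and 10% missed days. The 14-day baseline and Week 6 were both scaled to 7 days. Power was again equal or higher throughout: 0 to about 7 points at 0.10 and 0 to about 14 at 0.025.

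**6. Scaling one side only.** With a scaled baseline and a raw post-baseline sum, a steady man shows 6/7 − 1 = −14% with 6 recorded days, −29% with 5 and −43% with 4. At 10% missed days the average false reduction is about 10 points.

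**The case against.** **Bias against placebo.** A reader might infer that regression to the mean biases the primary comparison. It does not. Baseline is fixed before randomisation and the rule is the same in every arm, so its effect is expected to be equal across arms and type I error is not inflated. This stands in full.

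**Departure from the protocol.** A reader might set the 14 days beside the statement in SAP 6.9 that "there were no changes to methods planned in the protocol" and infer an undeclared change. The documents do not show one. The protocol collects 14 days to arrive at a weekly baseline, never says they are averaged, and refers to the SAP for full analyses.

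**The 14-day mean is not a cure.** This also stands. The near-zero mean change at a median of 14 is partly cancellation: men who qualified on one week only show a false increase of +3% to +51% with 14 days (step 5 settings). The median change over all men is still −1% to −21% in the step 4 settings, though closer to zero than under the SAP rule in every one. Nor does the SAP rule always produce a false reduction; at high rates its mean change is positive.

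**Variance need not fall.** Correct near the entry threshold, but power did not fall in any setting.

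**Switching can help.** If the second week fails only through missed entries, moving to a fuller week corrects an undercount. Scaling to 7 days deals with that directly. Switching also keeps the analysed baseline at or above the entry count, which a 14-day mean will not always do.

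**A mismatched fix would harm.** Rescaling baseline alone would add the false reduction in step 6. The change is sound only if both sides are scaled.

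**Conclusion.** The concern holds as a matter of efficiency and of within-arm description, not of validity. The rule selects the denominator of the primary endpoint partly on noise and ignores half of the baseline diary. The cost is 0 to about 7 points of power at one-sided 0.10 and 0 to about 14 at 0.025, together with distorted within-arm changes and paired tests.

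These sizes rest on assumed rates and variability that the documents do not give, and on a Week 6 comparison rather than the full MMRM or the slope tests. With low variability the loss is negligible. The change is worth making because it is cheap and no setting tried showed a loss of power.

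**What to change.** In SAP 6.1.1 and 6.3.1:

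- Define baseline weekly frequency, for every man, as 7 times the mean daily count of moderate to severe hot flashes over all recorded days of the 14-day screening diary. Compute baseline severity from the same days.
- Define each post-baseline week as 7 times the mean daily count over its recorded days, keeping the 4-day minimum, so that numerator and denominator share one scale.
- Delete week switching from the main analysis, leave the eligibility check unchanged, and keep the one-week rule as a sensitivity analysis.

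Settle this before the unblinded Week 6 analysis. The cost is SAP wording and programming, with no new data.

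Downsides to accept:

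- The SD rises by about 1–7% in some settings where most men sit near 12 a week, and by up to 13% (53.1 to 60.2) in the noisiest setting with a threshold of 28.
- Some men will have an analysed baseline below 12 a week.
- Regression to the mean is reduced overall but not removed, and men who qualified on one week only will tend to show an increase.

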### **9.3.1 Primary Analyses**

#### **9.3.1.1 Hot Flash Frequency, Week 6 (Day 42)**

Mixed models repeated measures (MMRM) analyses that incorporate, treatment, time, and the treatment\*time interactions will be the primary analytical method for the percentage change in the frequency of moderate to severe hot flashes. The percentage change from baseline in frequency of moderate to severe hot flashes in each active arm will be compared to the placebo arm at Week 6 (Day 42). The analysis will be handled in two ways within the MMRM framework: (1) the means analysis comparing the change from baseline to Week 6, and (2) the slope analysis comparing the rate of change from baseline to Week 6.

The primary endpoint in the study will be analyzed when the last patient reaches Day 42. However, the clinical site and patients will remain blinded through the completion of the Day 84 efficacy assessments and the follow up safety visits.

Each subject's hot flash frequency will be summed on a weekly basis. Because the MMRM is the primary analytical method, it will be possible to estimate Week 6 changes from baseline by incorporating the preceding weeks' data, e.g., Week 6 estimates will incorporate data from baseline and Week 1 through Week 6. Analyses will be performed for the EE (EEIA) populations.

If the MMRM model does not converge or has poor fit, T-tests or non-parametric tests, if the data are deemed non-normally distributed, will compare changes over time within (Paired T-test or Wilcoxon sign-rank test) an arm and between (T-test or Wilcoxon rank sum test) each active arm and the placebo arm, respectively.

The Hochberg procedure (Hochberg Y, 1988) will be applied to control for the multiple comparisons associated with the comparisons between the two dose arms and placebo and the two different MMRM analyses (means, slope) in the primary analyses of frequency of hot flashes in Stage 1. The analyses for Stage 2 will be treated similarly to address the multiplicity of the MMRM analyses. Note that the placebo arm in Stage 2 comprises a cohort of subjects distinct from those placebo subjects that were enrolled during Stage 1.

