#### 6.1.2 Handling of Dropouts and Missing Data

Subjects must have entered hot flash data (frequency and severity) for 4 or more days in a given week for their data to be considered non-missing. No other imputation procedures will be used to impute missing data. If a subject enters that there are no hot flashes to report on a given day, then this will be considered a data point equal to zero. If a subject does not report any hot flash information across consecutive days,

the data management team will be alerted to query the situation. From a data perspective, if a subject fails to report hot flash information on a given day, then that day will be recorded as missing.

For determining whether adverse events (AEs) are treatment-emergent when the start date of the AE is a partial date, refer to Section 6.4.1.

For determining whether a medication is a prior medication or concomitant medication, refer to Section 6.2.5.

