Additional prespecified analysis of the data will be conducted regardless of whether the MMRM model(s) converge, and will be considered the definitive tests for significance in the event the MMRM model(s) do not converge:

• T-tests will be generated to compare the percentage change from baseline to each of Week 6 in the placebo arm to each of the 10 mg and 50 mg arms. If the data are determined to be non-normally distributed then the Wilcoxon rank sum test will be the definitive test of significance.

• Wilcoxon rank sum tests will be generated to compare the percentage change from baseline to Week 6 in the placebo arm to each of the 10 mg and 50 mg arms.

The SAS code for performing the MMRM analyses to test for a significant difference in the SLOPES of the percentage change in frequency of moderate to severe hot flashes between each of the dose arms and placebo by Week 6 (primary analysis week) is shown below. Note that these analyses will generate the remaining two of the four tests that are part of the primary analysis to which the Hochberg procedure will apply.

The where statement in PROC MIXED has been used to simplify the interpretation of the output so that one model will be run for the 10 mg versus placebo slope analysis and a separate one for the 50 mg versus placebo slope analysis through Week 6. Variable have the same meaning as defined in the above analysis.

PROC MIXED DATA=XXX; CLASS subjid tx; MODEL cfb= tx week tx\*week / s; RANDOM intercept week/ type=AR(1) sub=subjid g; WHERE tx in (10, P) and week le 6; /\* repeat for 'tx in (50, P)' \*/ RUN;

This model allows for both the intercept and the slope to differ randomly for each subject but the overall p-value for the interaction term is interpreted as a test of the slope between the stated active arm and placebo. Note, if the p-value is significant, the estimated coefficients must be in the appropriate direction to conclude the result is in favor of the active dose arm.

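### Weekly hot flash frequency is an unscaled sum over 4 to 7 reported days, so the primary endpoint counts an unreported diary day as zero

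*SAP*

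**What the plan says.** SAP 6.3.1 (Data Handling) defines a week as 7 days, for example Days 36 to 42 for Week 6, and counts it as non-missing if at least 4 days were recorded. The count for a qualifying period is defined in these words: "the weekly frequency of moderate and severe hot flashes will be the sum across those days of the number of moderate to severe" events. Percentage change is the week's reported count minus the baseline reported count, divided by the baseline reported count. Protocol 9.3.1.1 says only that each subject's "hot flash frequency will be summed on a weekly basis".

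SAP 6.1.2 separates two kinds of day. An entry of no hot flashes is a real observation: "then this will be considered a data point equal to zero". An absent entry is not: "if a subject fails to report hot flash information on a given day, then that day will be recorded as missing". It adds: "No other imputation procedures will be used to impute missing data".

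The diary rule in Protocol 6.2.1 covers screening only: "Must be at least 80% compliant during the screening period". Protocol 8.2 turns this into "at least 11 of the 14 days". After baseline the only stated diary threshold is 4 of 7 days. The 80% requirement in the EE and EEIA populations concerns taking study drug.

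**The concern.** In a plain sum, a missing day and a zero day contribute the same amount, so 6.3.1 undoes the distinction that 6.1.2 draws. An incomplete post-baseline week looks like improvement, and an incomplete baseline week looks like worsening.

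No other part of the plan would show this. The mixed models take the distorted weekly value as observed data. The additional tests ("T-tests will be generated to compare the percentage change from baseline", and the Wilcoxon equivalents) use the same percentage change. So do the ITT sensitivity analysis and, with mild events added to the count, the all-severity one.

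This is the only primary endpoint. The option not to start Stage 2 rests on its statistical significance (SAP 6.7), and the ordered secondary endpoints are gated behind it (SAP 6.3.1).

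A smaller gap concerns severity. Post-baseline severity is divided by the number of hot flashes, so a week with none is 0/0. The day-level zero rule does not define that ratio, and the SAP gives it no value. If such weeks became missing, complete responders would lose their severity value for that week. Their frequency would still be a valid -100%.

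**Working it through.** **Inputs from the documents.** 7-day week, 4-day minimum and the percentage-change formula (SAP 6.3.1); 11 of 14 screening days (Protocol 8.2); 30 per arm, one-sided 0.10, active 40% below placebo (SAP 6.1.4). The plan gives no figure for the effect of missing days, so there is none to reproduce.

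**Step 1: one subject (exact).** Let R be the true post/baseline ratio of daily rates and k the number of reported days. Observed change = 100 × (R × k_post / k_base − 1).

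| R | k_base | k_post | Observed | True |
|---|---|---|---|---|
| 1.0 | 7 | 6 | -14.3% | 0% |
| 1.0 | 7 | 5 | -28.6% | 0% |
| 1.0 | 7 | 4 | -42.9% | 0% |
| 1.0 | 4 | 7 | +75.0% | 0% |
| 0.6 | 7 | 4 | -65.7% | -40% |
| 1.5 | 7 | 4 | -14.3% | +50% |

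Example: 28 per week at baseline is 4 per day. At the same rate, 4 reported days give 16, and (16 − 28)/28 = -42.9%. Scaled, 16 × 7/4 = 28, a change of 0%.

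The 4-day baseline week is possible because 11 days can split as 7 + 4. Note that 11/14 = 78.6%, just under 80%. If 12 days were required, the worst split would be 7 + 5 and the figure 7/5 − 1 = +40%.

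**Step 2: arm means (exact, if baselines are complete and completion is unrelated to rate).** False difference = 100 × R × (gap in mean reported days)/7.

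- One-day gap: 14.3 points at R = 1.0; 11.4 at R = 0.8.
- At R = 0.8, a gap of 0.45 day gives 5.1 points and a gap of 1.15 days gives 13.1.
- A mean of 6.2 days in both arms multiplies a true difference by 6.2/7 = 0.886, so 32 points becomes 28. If baseline weeks follow the same mix (55/20/15/10% with 7/6/5/4 days), the mean factor is 0.886 × 1.168, about 1.03. The cost is then noise rather than shrinkage.

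**Step 3: error rates (illustrative; all distributional inputs assumed).** Thirty per arm; baseline rate log-normal, mean 25 per week, log-SD 0.5, floor 12; Week 6/baseline ratio log-normal, mean 0.8 under the null, log-SD 0.2 to 1.0; Poisson counts; 8,000 trials per setting for the single test. Mean reported days of 6.65, 6.20 and 5.50 come from 7/6/5/4-day mixes of 75/17/6/2%, 55/20/15/10% and 25/25/25/25%. The single test is a one-sided Week 6 t-test at 0.10. The four-test Hochberg family (4,000 trials) uses t-tests on Week 6 values and on per-subject slopes as stand-ins for the planned mixed models.

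| Mean days, placebo vs active | Single test, false positive | Hochberg family, any false win |
|---|---|---|
| Equal | 0.10–0.11 | 0.07–0.09 |
| 6.65 vs 6.20 | 0.15–0.25 | 0.08–0.18 |
| 6.65 vs 5.50 | 0.24–0.63 | 0.13–0.54 |
| Scaled to 7 days, all settings | 0.10–0.11 | 0.06–0.09 |

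For power, the active ratio was 0.48 (40% below 0.8) with the 6.20-day mix in both arms. The unscaled sum lost 0 to 4 points at 0.10 and 1 to 9 points at 0.025, the strictest Hochberg step. At log-SD 0.5 with the 6.20-day mix at baseline too, power was 0.90 unscaled against 0.94 scaled at 0.10, and 0.70 against 0.79 at 0.025.

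**The case against.** The strongest reply is that false positives require completion to differ between arms in a double-blind trial, among men who passed a diary run-in. With equal completion, error is controlled and the power loss is modest. The larger gap in the table is an invented mix. If placebo subjects under-report instead, the same gap makes the test conservative, with a false-positive rate of 0.001 to 0.03. Queries on consecutive unreported days would also catch many short weeks: of the 35 ways to miss three days in a week, 25 include adjacent days. All of this stands. It limits how likely and how large the harm is, but it does not correct the formula.

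A second reply is that the SAP imputes nothing: it sums the reported days, and the zero is only a consequence. That is fair as to wording, but the result is the same as zero imputation. Scaling in turn fills the gap with the subject's own mean, so the sentence ruling out other imputation must be reconciled with it.

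A third is that entry is event-driven, so unreported days may be quiet ones. If every quiet day went unreported, then under the assumed rates at log-SD 0.2 a true difference of about 34 points would read as about 26 scaled and 32 unscaled. With half unreported, it would read as 31 and 33.5. This is a real cost of scaling. However, the SAP provides an explicit no-hot-flash entry and classes an absent entry as missing, so scaling follows its own definition. The risk is a reason to report both versions.

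**Conclusion.** The concern holds. As written, the primary endpoint treats unreported days as zero hot flashes, contrary to the SAP's own distinction between zero and missing, and no planned analysis would reveal it. The per-subject distortion is exact: -14% to -43% at an unchanged rate with a complete baseline, and up to +75% with a 4-day baseline. The -43% is the worst false improvement for an unchanged rate only; in points the artefact is smaller for improvers (25.7 at R = 0.6) and larger for worseners (64.3 at R = 1.5). The between-arm bias depends on completion rates that the documents do not give. The error rates above show what could happen under stated assumptions, and the bias can go in either direction. Because the rule defines the sole primary endpoint and informs the Stage 2 decision, it should be corrected before analysis. The severity point is a missing detail, and the conclusion does not depend on it.

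**What to change.** - In SAP 6.3.1 and Protocol 9.3.1.1, define weekly frequency as 7 × (sum over reported days / number of reported days), for the baseline week and every later week. Keep the 4-day minimum and count entered no-hot-flash days as reported zeros.
- In SAP 6.1.2, cross-refer the sentence on imputation to this definition.
- Keep the unscaled sum as a sensitivity analysis, and tabulate reported days per week by arm.
- State the severity value for a week with at least 4 reported days and no hot flashes, for example 0 (a change of -100%). Add a sensitivity analysis under another convention: the scale runs from 1 to 3, so from a baseline of 2 an all-mild week is -50% while a week with none would be -100%.

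The cost is a few sentences of wording, two lines of derivation code and two sensitivity runs. No new data are needed, and subjects with complete diaries keep the same frequency values.
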